#### **8.4.2.2    *Subject and Graft Survival***

The endpoint of subject and graft survival at 6, 12 and 24 months post-transplant will be summarized within each treatment group using point estimates of the proportion of subjects surviving with a functioning graft, and the corresponding 95% CIs. The proportion of subjects who die, proportion of subjects who have a graft loss, and the proportion of subjects who experience the following outcomes will each be summarized using point estimates and 95% CI within each treatment group.

- Overall graft loss rates at 6, 12 and 24 months
- Rates of death with a functioning graft at 6, 12 and 24 months;
- Rates of pure (death-censored) graft loss at 6, 12 and 24 months.

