4.2 Secondary Endpoint

The two treatment groups will be compared for all secondary endpoints.

Acute Rejection

- Treatment differences in the incidence of CSBPAR at 6, 12 and 24 months post transplant, in the belatacept + EVL versus TAC + MMF treatment groups.
- Time to CSBPAR.
- Treatment differences in the severity grades and therapeutic modalities used to treat all episodes of CSBPAR at 6, 12, and 24 months post-transplant:
 - Severity: To be assessed by each local pathologist using the 2007 update to the Banff 97 classification of renal allograft pathology).

- Treatment regimen: Categorical analysis of CSBP/AR episodes by treatment received, including: a) corticosteroids; b) lymphocyte depleting therapy; c) renal replacement therapy; d) plasmapheresis; e) IVIg; f) rituximab.

Subject and Graft Survival

- Proportion of all subjects who survive with a functioning graft at 6, 12 and 24 months post-transplant.
- Proportion of all subjects who experience death by 6, 12 and 24 months post-transplant.
- Proportion of all subjects who experience graft loss by 6, 12 and 24 months post-transplant.
- Time to event analysis of death or graft loss.

Renal Function

- Absolute (mean and median) cGFR values at 3, 6, 12 and 24 months post-transplant, as determined from the 4-variable Modification of Diet in Renal Disease (MDRD) formula.
- The mean changes from Month 3 cGFR at 6, 12, and 24 months post-transplant.
- Slope of the change in cGFR from Month 3 to Months 6, 12 and 24 post-transplant.
- The mean urine protein to creatinine ratio ($U_{Pr/Cr}$) at 3, 6, 12 and 24 months post-transplant.

Donor Specific Anti-HLA Antibodies (DSA)

- The percentage of subjects with, and titers of pre-existing (pre-transplant) and *de novo* (post-transplant) anti-HLA DSA on Day 1 (pre-transplant, pre-dose), and at Months 12 and 24, respectively.
- Characterization of any *de novo* DSA detected by IgM and IgG classes, and by the presence or absence of complement fixing properties.

Safety and Tolerability of each Treatment Regimen

- Incidence of all AEs and SAEs at 6, 12, and 24 months post-transplantation.
- Incidence of ESI at 6 months, 12 months, and 24 months
- Description and incidence of clinically significant changes in vital signs.
- Description and incidence of laboratory test marked abnormalities.

Cardiovascular and Metabolic Co-Morbidities

- Incidence of New Onset Diabetes After Transplantation (NODAT) at 6, 12, and 24 months post-transplant.

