6 STUDY PERIODS, TREATMENT REGIMENS AND POPULATIONS FOR ANALYSES

6.1 Treatment Regimens

Approximately 70 subjects (n=35 per arm) receiving de novo kidney transplants will be randomized (stratified by study site/center) in a 1:1 ratio to 1 of the following 2 treatment groups:

- Thymoglobulin + Belatacept + Everolimus.
- Thymoglobulin + Tacrolimus + MMF.

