7 STATISTICAL ANALYSES

7.1 Modifications to the Analyses Specified in the Protocol

Due to the reduction in sample size resulting from premature termination of enrollment as of 31 December 2016, it has been deemed appropriate to revise selected statistical analyses specified in the study protocol [Section 8](#). The following modifications to and clarifications of the analyses have been made:

- 1) All analyses will be performed for the whole study treatment period (i.e. 24 months), including analyses at 6 or 12 months.

- 2) Treatment differences will be produced only for the endpoints specified in the sections of this SAP itemized below, instead for all study endpoints.
- 3) Analysis of acute rejections:
 - a) The treatment differences in the severity grades and therapeutic modalities will not be calculated.
 - b) The sensitivity analyses using the per-protocol population will be performed if there are at least 10% of subjects with a protocol deviation in either treatment groups.
 - c) The sensitivity analyses using the as-treated population will be performed if there are at least 10% of subjects in either treatment group for whom the as-randomized treatment group is different from the as-treated treatment group.
 - d) The sensitivity analysis using right censoring at the time of discontinuation from assigned therapy will not be produced. Acute rejections occurring more than 56 days after the last dose date will be flagged in the listing.
 - e) The descriptive summaries by treatment group for cGFR, graft and subject survival, donor specified antibodies, infection and malignancy at Month 12 for subjects with and without AR by Month 6, and at Month 24 in subjects with and without AR by Month 12, will not be produced. The information regarding these parameters will be included in listings that correspond to the specific analyses of these endpoints.
- 4) Analysis of subject and graft survival:
 - a) A listing including all subjects who died or lost their graft will be produced. Corresponding summaries, treatment differences and time to event analysis will be produced if there are at least 5 subjects across treatment groups who died or experienced graft loss during the 24 Month treatment period.
 - b) Any summaries mentioned above, if to be produced, will only be produced for the whole 24 Month treatment period. The corresponding analyses at 6 and 12 months will not be produced.

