7.2 General Methods

All analyses of efficacy and safety endpoints will be summarized descriptively by the two treatment groups. No statistical tests will be performed.

Randomization to the study will be stratified by site only. Any within-treatment confidence interval (CI) for the proportion analyses will be computed using normal approximation, if the number of the events in that treatment group is at least 5. Otherwise, a CI calculated using an exact method will be provided. Any between-treatment CI for the proportion difference analyses will also be computed using normal approximation, if the number of the events in each individual treatment group is at least 5. Otherwise, a CI using an exact method will be provided.

For time to event analyses, if a patient does not experience an event, the censoring will be done at the last follow-up date if the subject discontinues prematurely; otherwise, censoring will be

done at the last dose date if the subject completed the 24 month-treatment period, unless specified otherwise.

The following table provides an overview of the primary and key secondary analyses to be performed.

Table 7.2-1: Overview of Primary and Key Secondary Analyses

Measure of Interest	Analysis Method
Proportion of subjects who experience a CSBPAR at 6, 12 and 24 months post-transplant	Point estimate of the proportion and 95% CI [*] within each treatment group at 6 months.
Difference in the incidence of CSBPAR between arms, at 6, 12 and 24 months post-transplant	Point estimate and 95% CI [†] for the difference between the two arms
Time to first CSBPAR	Kaplan-Meier (KM) estimates of survival functions. Hazard Ratio and 95% CI [§]
Proportion of Subjects who survive with a functioning graft at 24 months post-transplant	Point estimate of the proportion and 95% CI [*] within each treatment group at 24 months (to be produced if there are at least 5 subjects across treatment groups who died or experienced graft loss)
Time to death or graft loss	KM estimate of subject and graft survival Hazard Ratio and 95%CI [§] (to be produced if there are at least 5 subjects across treatment groups who died or experienced graft loss)

* Confidence Interval Formula: Exact (Clopper-Pearson)

† Confidence Interval Method: Score (Wilson)

§ Using Cox Proportional Hazard model

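### The 24-month survival proportions, intervals and difference are withheld below 5 pooled deaths or graft losses, though the plan's own exact methods would cover them

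*SAP*

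**What the plan says.** The SAP keeps survival as a secondary endpoint. Section 4.2 lists "Proportion of all subjects who survive with a functioning graft at 6, 12 and 24 months post-transplant", with death and graft loss at the same times. Protocol 8.4.2.2 summarises it within each arm "using point estimates of the proportion of subjects surviving with a functioning graft, and the corresponding 95% CIs" and sets no minimum number of events.

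SAP Section 7.1, item 4a, changes this. It promises that "A listing including all subjects who died or lost their graft will be produced", and then that the survival summaries, the between-arm differences and the time-to-event output "will be produced if there are at least 5 subjects across treatment groups who died or experienced graft loss" within 24 months. The same condition is attached to the Table 7.2-1 row for "Proportion of Subjects who survive with a functioning graft at 24 months post-transplant" and governs all the analyses in 7.6.2.1. Item 4b limits any such summaries to Month 24: "The corresponding analyses at 6 and 12 months will not be produced".

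Four other parts of the SAP bear on the point:

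- Section 7.2 calls for an exact interval for a proportion when an arm has fewer than 5 events. Table 7.2-1 names Clopper-Pearson within arms and a Wilson score interval for the CSBPAR difference.
- Section 7.6.1.1 reports CSBPAR proportions, intervals and the difference with no event threshold.
- Section 7.6.2.2 analyses a composite of CSBPAR, death or graft loss once there is at least one CSBPAR and at least one death or graft loss.
- Section 7.7 plans two summaries of death and of graft loss, with frequencies and exposure-adjusted rates by arm. It states no event threshold.

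**The concern.** A threshold on events makes sense for a Kaplan-Meier curve or a hazard ratio, which say little with three or four events. It makes less sense for a proportion with an exact interval, which is valid at any count, including zero.

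The research hypothesis claims acceptable rejection and overall safety in line with standard of care. Survival with a functioning graft is a main part of that claim. Under item 4a, whether it is estimated with an interval depends on the event count. Two informative results fall below the gate: a reassuring one with few or no events, where the upper limit is what matters, and a lopsided one such as 4 versus 0. In either case the report would lack the planned proportion, its interval and the difference.

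**Working it through.** **Inputs.** The SAP plans "Approximately 70 subjects (n=35 per arm) receiving de novo kidney transplants". The threshold is 5 subjects with death or graft loss, both arms pooled, over 24 months. The documents give no expected risk of death or graft loss, so every risk below is an assumption.

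**1. Reproduce the plan's own precision figures (SAP Section 5).** Clopper-Pearson with n = 35 and x = n × p gives 0.2% to 16.4% at 3.8% and 0.1% to 15.1% at 3%, as stated. For the difference of 3% and 3.8%, the Newcombe interval (built from two Wilson score intervals, no continuity correction) gives -13.2% to 11.3%, as in Table 5-1. Of the variants tried, only this one matches, so it is used below.

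**2. Compare with CSBPAR.** The planning rates imply 35 × 0.038 = 1.33 and 35 × 0.03 = 1.05 events, about one per arm. The plan reports intervals and a difference for CSBPAR at such counts. The same counts of death or graft loss would total about 2 and fall below the gate.

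**3. Chance of falling below the gate.** With X ~ Binomial(70, p), the chance is P(X ≤ 4). For p = 5% the terms for 0 to 4 events are 0.0276 + 0.1016 + 0.1845 + 0.2201 + 0.1941 = 0.728.

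| Assumed 24-month risk | P(fewer than 5 of 70) |
|---|---|
| 3% | 94% |
| 5% | 73% |
| 6% | 59% |
| 8% | 33% |
| 10% | 16% |
| 15% | 1.5% |

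The chance is 50% at a risk of about 6.6%. With unequal arms, 10% versus 3% gives 52% and 10% versus 5% gives 39%. With only 60 evaluable subjects the 5% figure becomes 82% and the 50% point moves to 7.7%. None of these figures includes events imputed under SAP 8.3.

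**4. What could be reported below the gate.**

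- 0/35: exact 95% CI 0% to 10.0%.
- 0/35 versus 0/35: Newcombe interval for the difference -9.9 to 9.9 points.
- 4/35 = 11.4%: exact 95% CI 3.2% to 26.7%.
- 4/35 versus 0/35: difference 11.4 points. The Wilson limits are 4.5% to 26.0% for 4/35 and 0% to 9.9% for 0/35. Lower limit: 11.4 - √((11.4 - 4.5)² + 9.9²) = -0.6. Upper limit: 11.4 + (26.0 - 11.4) = 26.0.

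The lower limit depends on the method: the Mee score interval for the same split is 1.0 to 26.0 points. Every one of these intervals can be computed and says something useful.

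**The case against.** The strongest reply is that little is hidden. Section 7.7 still tabulates deaths and graft losses by arm, with person-year rates, at any count. The composite in 7.6.2.2 has a much lower trigger and includes the same events. Below the gate there are at most four cases, all listed, so a reader who knows the arm sizes could work out n/N. The trial is descriptive, with no tests. The rule is disclosed as a change from the protocol, with the reduced sample size as its reason, and a pooled count favours neither arm. The 4-versus-0 split is also an extreme case: with four events and equal risk, all four fall in one arm with probability 2·C(35,4)/C(70,4) = 104,720/916,895, about 11%.

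Most of this stands and limits the severity. It does not close the gap. The safety summaries use the as-treated grouping, specify no interval or difference, and do not give the proportion surviving with a functioning graft. The composite mixes in rejection and needs at least one CSBPAR. Working from listings also means rebuilding the denominators, because SAP 8.3 counts some subjects of unknown status as events and drops the others. The smaller sample is a reason to gate curves and hazard ratios, not exact proportions.

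A reader might infer three stronger points that the documents do not support:

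- That the endpoint will probably go unestimated. This needs a pooled risk below about 6.6%, and no risk is stated. Imputed events under 8.3 could also raise the count; the SAP does not say whether they count toward the 5.
- That below the gate only a listing appears, with no rate. Section 7.7 contradicts this.
- That the threshold was chosen after looking at outcomes. Section 7.1 was added in SAP version 3.0, which aligns with a protocol revision dated after enrolment had closed in this open-label trial. Nothing in the documents shows that survival data informed the number.

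**Conclusion.** The concern holds in a limited form. Below 5 pooled events, the SAP withholds the Month 24 survival proportion, the death and graft-loss proportions, their intervals and the difference in survival. The protocol analysis has no such gate, and the SAP's own handling of sparse events and of CSBPAR shows that none is needed for these quantities.

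The chance that the gate applies runs from 94% to 1.5% as the assumed risk goes from 3% to 15%. These figures assume 70 evaluable subjects, independent events and no imputed events. Counts and person-year rates of death and graft loss remain available by arm in any case, so this is a minor reporting improvement and not a threat to the primary analysis.

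**What to change.** In SAP 7.1 item 4a, Table 7.2-1 and 7.6.2.1, remove the event condition from the Month 24 proportions. Whatever the count, report n/N and exact 95% intervals per arm, and the score interval for the between-arm difference, for death, graft loss and survival with a functioning graft. Section 7.6.2.1 now plans a difference only for survival, so the other two are small additions. Keep the 5-event condition for Kaplan-Meier, Cox and subgroup output, and say whether events imputed under 8.3 count toward it.

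Name the score method. The Section 7.2 text asks for an exact interval for a difference when events are few, while the Table 7.2-1 footnote names Wilson score, and the 4-versus-0 example shows that the choice can matter.

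The cost is one small table with wide intervals. The change does not restore Months 6 and 12, which item 4b drops at any count; if that stands, Section 4.2 should say so.

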### **Safety and tolerability of each treatment regimen**

- Incidence of all AEs and SAEs at 6, 12 and 24 months post-transplant;
- Incidence of ESI at 6, 12 and 24 months post-transplant;
- Description and incidence of clinically significant changes in vital signs;
- Description and incidence of laboratory test abnormalities.

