3.2 Secondary

The effects of each immunosuppressant regimen on the rates of acute rejection, subject and allograft survival and allograft function were to be evaluated as follows (endpoints to measure these objectives are described in further detail in protocol [Section 8.3](#)):

- The frequency and severity of CSBPAR at 12 and 24 months post-transplant.
- Rates of subject and allograft survival at 6, 12 and 24 months post-transplant.
- Changes in renal function and severity of proteinuria at 3, 6, 12 and 24 months post-transplant.
- The frequency and type of donor-specific, anti-HLA antibodies (DSA) detectable prior to, and at 12 and 24 months post-transplant.
- The safety and tolerability of each treatment regimen, as based upon the results of vital signs, and safety laboratory assessments, and cumulative rates of adverse events reported at 3, 6, 12 and 24 months post-transplant.

The frequency of cardiovascular and metabolic co-morbidities reported at 3, 6, 12 and 24 months post-transplant.

[REDACTED]

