 - c) Subject and allograft survival rates among those subjects who did and those who did not experience CSBPAR. This analysis will be produced only if there are at least 5 subjects across treatment groups who died or experienced graft loss during the 24 month-treatment period.
- 5) Analysis of the composite endpoints of CSBPAR, death, or graft loss will be produced only if there is at least one CSBPAR and at least one death or graft loss. These analyses will include the proportion of all subjects who experience CSBPAR, death, or graft loss at 12 and 24 months and a time to event analysis of the composite endpoint of CSBPAR, death, or graft loss.
- 6) All safety analyses will only be produced for the whole 24 Month treatment period. The corresponding safety analyses at 6 and 12 months will not be produced.
- 7) Analysis of immunogenicity: The protocol specifies summaries of titers of detectable anti-belatacept antibodies at Weeks 8, 12, and 24 post study termination (subjects who discontinue belatacept only). Instead of descriptive statistics, a listing will be provided for all positive subjects. Similarly, the analysis of descriptive statistics for titers of detectable anti-belatacept antibody will not be produced.

- 8) Analysis of any clinical consequences of CSBPAR (and associated changes in the expression of exploratory gene sets associated with acute rejection) at 6, 12 and 24 months post-transplant will be presented as follow:
 - a) The extent to which renal function recovered to the pre-rejection baseline will include the serum creatinine values related to CSBPAR in the corresponding listing.
 - b) The percentage of subjects who, post-CSBPAR, are reported to have developed infection or malignancy will not be summarized. Instead, a listing will be provided.
 - c) The percentage of subjects with, and titers of detectable, de novo (post-transplant) anti-belatacept antibodies will not be summarized. Instead, this information will be included in a listing of immunogenicity results with corresponding belatacept concentrations and selected laboratory parameters and events of special interest.
 - d) The subject and graft survival rates among those subjects who did, and those who did not experience CSBPAR will be provided only if there are at least 5 subjects across treatment groups who died or experienced graft loss during the 24 month-treatment period.

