APPENDIX 5 DOCUMENT HISTORY

Table 9-3: Document History

Version Number	Author(s)	Description
1.0	[REDACTED]	Original Issue
2.0	[REDACTED]	Syntactical edits and clarifications in support the revised study design articulated in IM103177 Revised Protocol 03, incorporating Amendment 04.
3.0	[REDACTED]	
Syntactical edits and clarifications in order to align the revised study design articulated in IM103177 Revised Protocol 06, incorporating Amendments 05, -06 and -07 in several sections. The changes include the following:
 
 1. Section 1: 
 a. alignment with the protocol b. addition of clarifications regarding the schedule of the analyses 2. Section 2: 
 a. alignment with the protocol language b. updated design according to protocol c. Included the amendments summary 3. Sections 3, 4 and 5: 
 a. alignment with the protocol language b. Section 4: removal of the headers “Key Secondary Endpoints”, “Other secondary endpoints” and subsection [REDACTED] to align with the protocol 4. Section 6 
 a. alignment with the protocol language b. addition of clarification for the as treated population c. [REDACTED] 5. Section 7 
 a. Addition of Section 7.1 summarizing the modifications to the analyses specified in the protocol b. The sensitivity analysis from Section 3) was moved to Section 7.6.1 in order to keep analysis related to AR in the same section. Also, the right censoring was included in the sensitivity analysis. c. alignment with the protocol language d. alignment between CRF and demographics and baselines characteristics in Section 7.4.2 e. added clarification for the safety conventions that will be used in Section 7.4.3 f. added “Serious adverse events and related serious adverse events with death as an outcome following EudraCT” in Section 7.7.1 g. added “of subjects meeting them for each of the analysis periods. All laboratory values of a lab parameter (independently of study period) for subjects with at least one marked abnormality for this parameter will be listed” in Section 7.7.2

Table 9-3: Document History

Version Number	Author(s)	Description
		6. Section 8 [REDACTED]
		b. added table with different range days for time points in Section 8.4

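### SAP 7.1 item 6 drops the Month 6 and Month 12 AE, SAE and ESI incidence that protocol 8.3.2 and SAP 4.2 still declare as secondary endpoints, and the smaller sample does not explain why

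*SAP*

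**What the plan says.** Protocol 8.3.2 (Revised Protocol 06, 14 August 2017) names two incidence endpoints under safety and tolerability: "Incidence of all AEs and SAEs at 6, 12 and 24 months post-transplant" and "Incidence of ESI at 6, 12 and 24 months post-transplant". SAP 4.2 repeats the ESI endpoint at the same three months and gives the other as "Incidence of all AEs and SAEs at 6, 12, and 24 months post-transplantation". SAP 3.2 states the matching secondary objective in terms of "cumulative rates of adverse events reported at 3, 6, 12 and 24 months post-transplant". SAP 8.4 defines Month 6, 12 and 24 event windows for adverse events, ending on Days 168, 364 and 728.

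SAP 7.1 item 6 then says "All safety analyses will only be produced for the whole 24 Month treatment period" and adds "The corresponding safety analyses at 6 and 12 months will not be produced". It attaches no condition. The reason given for the list of modifications that contains item 6 is "Due to the reduction in sample size resulting from premature termination of enrollment as of 31 December 2016". SAP Appendix 5 records, under version 3.0, "Addition of Section 7.1 summarizing the modifications to the analyses specified in the protocol".

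**The concern.** A declared secondary endpoint with three time points is reduced to one, while the sections that declare it and define its windows are left unchanged. The protocol endpoint goes two-thirds unreported, and a programmer working from SAP 4.2 and 8.4 would build tables that item 6 says not to build.

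The early time points carry clinical information here. Thymoglobulin is confined to the first 10 days, belatacept is given at 10 mg/kg to Week 12 and 5 mg/kg afterwards, and the everolimus trough target is higher for the first 3 months. If an excess of SAEs or serious infections occurs in that period, a 24-month proportion mixes it with some 18 months of lower-intensity treatment. What is at stake is complete reporting of declared safety endpoints. Error rates are not involved, because no tests are planned.

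**Working it through.** **1. What is declared and what survives**

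| Output | Months 6 and 12 | Source |
|---|---|---|
| Subjects with AE, SAE or ESI: declared | Yes | Protocol 8.3.2, SAP 4.2 |
| Adverse-event windows | Yes, Days 168 and 364 | SAP 8.4 |
| Subjects with AE, SAE or ESI: produced | No | SAP 7.1 item 6 |
| Acute rejection (CSBPAR) proportion | Produced | SAP 7.6.1.1 |
| NODAT incidence | Produced | SAP 7.6.2.5 |
| Death and graft loss | Not produced; Month 24 only, if at least 5 subjects have an event | SAP 7.1 item 4 |

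**2. Do the retained tables replace it?** SAP 7.7.1.3 gives total events and exposure-adjusted rates for AEs and SAEs in 6-month intervals. These are counts of occurrences: the SAP's own example divides 8 episodes by 40 years to get 20 per 100 patient-years. The number of subjects affected by Day 168 cannot be recovered from such a figure, and ESIs are not tabulated there as a category. SAP 7.7.1.2 has first-occurrence rates for SAEs and AEs of clinical interest, but for the Month 24 analysis. It mentions later intervals without defining any.

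**3. Does the sample size explain it?** First, the plan's own precision figures at 35 per arm (SAP Section 5), reproduced:
- Clopper-Pearson, x = 0.038 × 35 = 1.33: 0.21% to 16.37% (SAP: 0.2% to 16.4%).
- Clopper-Pearson, x = 0.03 × 35 = 1.05: 0.09% to 15.14% (SAP: 0.1% to 15.1%).
- Difference by the Wilson score method without continuity correction: -13.17% to 11.32% (SAP: -13.2% to 11.3%).

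A within-arm Clopper-Pearson interval depends on the count and n, not on the month. At n = 35: 0 events gives 0 to 10.0%, 5 gives 4.8% to 30.3%, 8 gives 10.4% to 40.1%, 13 gives 21.5% to 55.1%. The plan accepts this precision at Months 6 and 12 for CSBPAR, where it assumes rates of only 3% to 3.8%.

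**4. What the extra columns could and could not show.** The documents give no AE rates, so this is an illustration on assumed values: first-event rate 0.60 per year to Day 168 and 0.15 per year afterwards; 10% stopping treatment uniformly over Days 0 to 168; follow-up to the earlier of last dose + 56 days and the end of the window. The proportion for a subject followed to time t is 1 - exp(-cumulative hazard). The multipliers for the other arm are also chosen values.

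| Other arm | Day 168 | Day 364 | Day 728 | Ratio to reference at 6/12/24 months |
|---|---|---|---|---|
| Reference | 0.236 | 0.289 | 0.377 | – |
| Early rate × 2 | 0.416 | 0.456 | 0.523 | 1.76 / 1.58 / 1.39 |
| Both rates × 1.65 | 0.359 | 0.430 | 0.539 | 1.52 / 1.49 / 1.43 |
| Late rate × 2.93 | 0.236 | 0.381 | 0.572 | 1.00 / 1.32 / 1.52 |

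In expectation, the Month 24 ratios (1.39 to 1.52) hide the timing and the Month 6 ratios (1.00 to 1.76) show it. In one trial of 35 per arm they would not show it reliably. With SE(log ratio) = √[(1-p₁)/(35p₁) + (1-p₂)/(35p₂)], the early-doubling case at Month 6 gives √(0.584/14.56 + 0.764/8.26) = √(0.0401 + 0.0925) = 0.364, so 1.76 has a 95% interval of 0.86 to 3.60. The other two are 1.52 (0.72 to 3.20) and 1.00 (0.43 to 2.32). All three overlap.

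**5. Timing.** Enrolment closed on 31 December 2016 (protocol 3.1), and randomisation is on Day 1. The last possible Day 168 is therefore 16 June 2017 and the last possible Day 364 is 29 December 2017. SAP 3.0 aligns with a protocol dated 14 August 2017, which is Day 227 for that last subject and 59 days after the last Day 168. The SAP's own date is not visible.

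**The case against.** The strongest reply has four parts.

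- **The change is disclosed.** Item 6 sits in the section written to record departures from the protocol, early events still enter the 24-month table, and AE, SAE and ESI listings are planned. This stands. It means nothing is concealed, but a listing is not a summary of a declared endpoint.
- **Trimming is not peculiar to AEs.** Item 4 drops the same months for death and graft loss, and NODAT is analysed with efficacy, so it is not a perfect comparator. This stands in part. Item 4 is tied to an event count, however, whereas item 6 is unconditional, and CSBPAR and NODAT show that 35 per arm was thought adequate for Month 6 and 12 proportions.
- **Small samples do limit what the early columns can show.** This stands for between-arm contrasts, as step 4 shows. It is a reason to label the figures descriptive, which the whole study already is.
- **SAP 7.7.1.2 may intend first-event interval rates for SAEs and ESIs.** Its reference to later intervals allows that reading. If it is meant, part of the loss is made good, but as rates and not as the declared cumulative incidence.

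A reader might also infer from the dates that the Month 6 tables were dropped after sight of open-label results. The documents do not support that. The dates bound the finished SAP 3.0 and not the decision. The sample-size cut was already in Amendment 06 (11 November 2016), and Amendment 07 says it aligned acute-rejection analyses with the SAP, so drafting may have begun before August 2017. For Month 12 the last Day 364 falls after 14 August 2017. Nothing shows that data drove the change.

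**Conclusion.** The point holds as one of incomplete reporting and internal inconsistency. For AEs, SAEs and ESIs, two of three declared time points are removed, the sections that declare them and define their windows are unchanged, and the stated reason does not separate these endpoints from CSBPAR and NODAT at the same 35 per arm. The retained interval table does not supply the proportion of subjects affected.

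The size is modest. The conclusion rests on the text alone. The modelled ratios rest on assumed rates and serve only to show why timing matters and why contrasts would be imprecise. The gain is mainly for SAEs and the summarised ESIs: if almost every subject has some AE by Month 6, the all-AE proportion adds little. It would be too strong to say that the early columns would distinguish an early from a constant excess in this trial, since the Month 6 intervals overlap.

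**What to change.** Amend SAP 7.1 item 6 to keep, at Day 168 and Day 364 beside Day 728, the number and proportion of subjects with any AE, any SAE, and each ESI that SAP 7.7.1.2 already plans to summarise: serious infections, serious viral infections, and infusion-related reactions (belatacept arm only, as defined there). Use the SAP 8.4 windows and label the figures descriptive. ESIs planned only as listings need no extra columns.

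The cost is two columns in planned tables, from data already collected. The downside is small counts: under the assumed reference rates, about 35 × 0.236 ≈ 8 subjects per arm would have a first event by Month 6 and 35 × 0.289 ≈ 10 by Month 12. Between-arm contrasts will be imprecise and should not be over-read.

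If the sponsor still prefers Month 24 only, SAP 3.2, 4.2 and 8.4 should be brought into line with item 6, and the study report should give the date of the decision and whether safety data by arm had been seen.
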